8.1. Screening Assessments

Information collected during the screening phase assessments represent key data that identify and define participant baseline status. This information is critical for evaluation of subsequent safety assessments.

Informed Consent

Informed consent will be obtained from the participant's parent/legally appointed representative prior to the initiation of any study procedures or study-specific data collection. The participant will provide their assent to participate in the study at the same time. Participants who turn 18 years old during the course of the study will provide their own informed consent.

Participants who give written consent will enter a screening period of up to 35 days. A participant may have treatment assigned when all screening procedures have been completed and eligibility criteria confirmed.

Screening Assessments

During the screening period the following assessments will be performed:

Demographic parameters will be captured: Date and year of birth, sex, race, and ethnicity.

Medical history/medication will be assessed as related to the exclusion criteria listed in Section [5.2](#). A complete medical history will be taken at the Screening Visit. Information

from the medical history is important to establish the baseline condition of the participant, and will impact the safety monitoring assessments during the study. Any significant medical conditions affecting the participant in the past 5 years should be recorded on the Medical conditions page of the eCRF. The history should include the following:

- Past or current conditions
- Prior surgical procedures
- Pharmacotherapy and chronic or current use of any medication or herbal preparation
- Prior use of belimumab
- Allergies and significant allergic reactions
- Significant infections, or history of recurrent infection, including urinary and respiratory tract infections
- Smoking history (current or previous smoker, number of cigarettes smoked per day)
- Cardiovascular medical history/risk factors (as detailed in the eCRF).

Pregnancy Test

A serum pregnancy test will be performed for females of child-bearing potential at the Screening Visit and a urine pregnancy test will be performed during each subsequent clinic visit. Refer to the pregnancy section (Section 8.9.5).

Full Physical Examination, Height, Weight, and Vital Signs

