The full physical examination will include complete assessment of all organ systems including assessments of the head and neck (including eyes, ears, nose, throat, and thyroid gland), skin, musculoskeletal (including evaluation of both small and large joints), neurological, respiratory, and cardiovascular systems, gastrointestinal system, and abdomen (including liver and spleen), lymph nodes and extremities.

Height and weight, and vital signs (systolic and diastolic blood pressure [sitting], heart rate, and body temperature) will be measured and recorded.

Electrocardiogram

A single 12-lead ECG will be obtained for screening purposes only as outlined in the SoA (see Section 1.3) using an ECG machine that automatically calculates the heart rate and measures PR, QRS, and QT intervals. If the screening ECG is abnormal, the Investigator may at their discretion exclude the participant from the study and/or contact the Medical Monitor to discuss the appropriateness of including the participant.

Laboratory Tests

The following laboratory tests will be performed by the central laboratory at screening, as related to the eligibility criteria described in Section 5.

- Autoantibodies (anti-dsDNA, ANA), complement (C3, C4) and CRP
- HIV, hepatitis B and Hepatitis C screen
- Immunoglobulins (IgG, IgA, IgM)
- Urinalysis (including drug and alcohol screen)
- Hematology, PT/PTT and blood chemistry
- Urine protein:creatinine ratio
- Pregnancy test (serum)
- NOTE: To maintain the volume of blood collection with local guidelines, the screening assessments for participants <30 kg will be split across 2 visits separated by a minimum of 2 weeks. There must also be a minimum of 2 weeks between the second screening and the Day 1 blood draws (see SRM for details). This may also apply to participants ≥ 30 kg according to local guidelines.

Disease Activity Index

The SELENA SLEDAI (Appendix 9) will be performed at screening to assess the level of SLE severity.

Suicidality Assessment

Possible suicidal behavior or ideation will be assessed at screening (see also Section 5.2).

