5.4. Baseline Definitions

For all endpoints, the baseline value will be the latest pre-dose assessment with a non-missing value, including those from unscheduled visits. If time is not collected, Day 1 assessments are assumed to be taken prior to first dose and used as baseline.

Parameter	Study Assessments Considered as Baseline		Baseline Used in Data Display		
	Screening	Day 1 (Pre-Dose)			
Efficacy					
SELENA-SLEDAI	X	X	Day 1		
Safety and Biomarker					

Parameter	Study Assess	Baseline Used in Data Display	
	Screening	Day 1 (Pre-Dose)	
Laboratory assessments (including hematology, urinalysis, chemistry, AntidsDNA/ANA and complement C3/C4)	X	X	Day 1
Biomarkers (including BLyS Protein, B-Cells, and immunogenicity)		X	Day 1

Note that the SELENA-SLEDAI total score is calculated by summing 24 individual items. The total score used as Baseline will be calculated from all available items at Day 1, but if individual items are missing, the Screening assessment for those items will be used.

Concomitant medications are considered to be present at baseline if the start date is prior to Day 1 and the end date is on or after Day 1. Medications with a start date on Day 1 are considered as being on-treatment (concomitant). For further details, see Section 13.2.1.

Adverse events (AE) are considered pre-treatment if the start date is prior to Day 1, or if the start date is on Day 1 but the AE start time shows that the event starts pre-dose. Treatment emergent AEs are defined in Section 13.2.2.

Unless otherwise stated, if baseline data is missing no derivation will be performed and baseline will be set to missing.

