5.5. Change from Baseline and Percentage Change from Baseline

Change from baseline for the visit of interest will be calculated as

Visit value – baseline value.

If either value is missing, the change from baseline will be missing.

Percentage change from baseline for a visit of interest will be calculated as

$$\frac{\textit{Visit value} - \textit{baseline value}}{\textit{baseline value}} \times 100.$$

Subjects with a baseline value of zero will not have a value calculated due to division by zero. If the baseline value is zero or missing, then the percentage change will set to missing.

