11.1.4. Change from Baseline

Change from baseline will be summarized by visit for the following:

- Immunoglobulin levels for all subjects [T4.02]
- B-cells for all subjects [T4.11]
- Autoantibody levels among subjects who were positive at baseline (ANA Index ≥80 titer; anti-dsDNA ≥ 30 IU/mL; CRP ≥ 4 mg/L) [T4.05]. Note that positive baseline assessments are assessed at a parameter level, e.g. the anti-dsDNA summary will include all subjects who were positive at baseline for anti-dsDNA.
- Complement levels among subjects with low values at baseline (C3<90 mg/dL; C4 < 13 mg/dL) [T4.08]. Note that low baseline assessments are assessed at a

parameter level, e.g. the C3 summary will include all subjects who were low at baseline for C3.

No statistical tests will be performed.

A figure of median change from baseline (+/- Interquartile Range) will be produced by visit for complement levels for subjects with low complement at baseline [F4.04].

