11.1.5. Percentage Change from Baseline

Percentage change from baseline will be summarized by visit for the following:

- Immunoglobulin levels for all subjects [T4.01]
- B-cells for all subjects [T4.10]
- Autoantibody levels among subjects who were positive at baseline (ANA Index ≥80 titer; anti-dsDNA ≥ 30 IU/mL; CRP ≥ 4 mg/L) [T4.04]. Note that positive baseline assessments are assessed at a parameter level, e.g. the anti-dsDNA summary will include all subjects who were positive at baseline for anti-dsDNA.
- Complement levels among subjects with low values at baseline (C3<90 mg/dL; C4 < 13 mg/dL) [T4.07]. Note that low baseline assessments are assessed at a parameter level, e.g. the C3 summary will include all subjects who were low at baseline for C3.

The B cell subsets that will be summarized are CD19+ Total B cells, B cells CD20+, Memory CD20+ CD27+, Naïve CD20+ CD27- and Plasmablasts CD27b CD38b.

No statistical tests will be performed.

Figures of median percentage change from baseline (+/- Interquartile Range) will be produced by visit for:

- Immunoglobulin levels for all subjects [F4.01]
- B-cells for all subjects [F4.05]
- Autoantibody levels among subjects who were positive at baseline (as described above) [F4.02].
- Complement levels among subjects with low values at baseline (as described above) [F4.03].

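### Numeric change in C3/C4 and anti-dsDNA is summarized only in children selected on the same pre-dose value that is then subtracted, so part of any apparent improvement is regression to the mean

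*SAP*

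**What the plan says.** **The subset.** SAP 11.1.4 summarizes change for "Complement levels among subjects with low values at baseline (C3<90 mg/dL; C4 < 13 mg/dL) [T4.08" and for "Autoantibody levels among subjects who were positive at baseline (ANA Index ≥80 titer; anti-dsDNA ≥ 30 IU/mL; CRP ≥ 4 mg/L) [T4.05". SAP 11.1.5 applies the same restriction to percentage change: "Complement levels among subjects with low values at baseline (C3<90 mg/dL; C4 < 13 mg/dL) [T4.07" for complement, and T4.04 for autoantibodies. Figures F4.02 to F4.04 follow it. Status is judged parameter by parameter. In the same lists, immunoglobulins and B cells are summarized for all subjects.

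**The baseline.** SAP 5.4 states that "the baseline value will be the latest pre-dose assessment with a non-missing value, including those from unscheduled visits", and its table shows Day 1 as the baseline displayed for anti-dsDNA/ANA and C3/C4. SAP 5.5 defines change as "Visit value – baseline value".

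**The second pre-dose sample.** Protocol 8.1 lists "Autoantibodies (anti-dsDNA, ANA), complement (C3, C4) and CRP" among the central-laboratory screening tests, and the Part A schedules mark them again on Day 1. Protocol 8.1 also says: "Participants who give written consent will enter a screening period of up to 35 days".

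**The endpoint.** Protocol 9.3.3 makes change in C3/C4 and anti-dsDNA at Weeks 12 and 52 a secondary endpoint on the ITT population, with no restriction by baseline status. SAP 11.1.1 says change will be evaluated for every biomarker in Table 6. SAP 2.1 declares no departure from the protocol analysis.

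**What covers everyone.** SAP 11.2 plans category shift tables for autoantibodies (T4.06) and complement (T4.09), in both directions. Listing L4.01 shows all values.

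**The concern.** A child enters the complement tables because one measurement was low. That measurement contains short-term fluctuation as well as the child's usual level, and selecting on it favours children whose fluctuation was downward that day. The next measurement will on average be higher with no treatment effect. Anti-dsDNA is the mirror image: selection on a high value is followed by a fall. CRP and ANA have the same structure, although they are not part of the protocol endpoint.

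In a controlled trial this would largely cancel between arms. Here there is no second arm. The artefact also runs the way belimumab is expected to act: the title of a cited adult study reports reduced autoantibodies and normalized low complement. For these markers the subset tables are the only planned numeric summaries of change, so the size of the pharmacodynamic effect would be read from a figure with a built-in favourable component.

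**Working it through.** **The plan's own figure.** The plan gives no effect size, SD or precision for this endpoint, so there is nothing to reproduce. The nearest arithmetic, the number to screen, is 28/(1 − 0.20) = 35 against 36 stated. That is close, and this point does not depend on it.

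**Inputs.** The selection rule, baseline rule and change formula come from the SAP sections above. Not given in either document, and therefore assumed: within-child correlation r between two visits (0.6 to 0.9), the share f of children below the cut (30 to 70%), an SD for C3 (25 mg/dL), and an SD for ln(anti-dsDNA) (1.0 to 1.5).

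**Step 1: expected change with no drug effect.** For a bivariate normal pair with equal SDs, selecting on the first value gives

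mean change = (1 − r) × λ × SD, with λ = φ(z)/f and z = Φ⁻¹(f).

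| Share low | λ | r = 0.6 | r = 0.7 | r = 0.8 | r = 0.9 |
|---|---|---|---|---|---|
| 30% | 1.159 | 0.46 | 0.35 | 0.23 | 0.12 |
| 50% | 0.798 | 0.32 | 0.24 | 0.16 | 0.08 |
| 70% | 0.497 | 0.20 | 0.15 | 0.10 | 0.05 |

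Entries are in SD units. Simulation with 2,000,000 draws per setting agreed, and gave 0.00 for change in all subjects.

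**Step 2: natural units.**
- C3 with SD 25: from 0.05 × 25 ≈ 1 mg/dL to 0.46 × 25 ≈ 12 mg/dL. With half low and r = 0.7 to 0.8, it is 4 to 6 mg/dL.
- Anti-dsDNA: the geometric-mean fall is 1 − exp(−(1 − r)λs), where s is the SD of the log. For 50 to 70% positive it runs from 1 − exp(−0.1 × 0.497 × 1.0) ≈ 5% to 1 − exp(−0.4 × 0.798 × 1.5) ≈ 38%.

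**Step 3: the shift table.** With half low and no drug effect, the chance that a low child reads normal later is arccos(r)/π: 30%, 25%, 20% and 14% for r = 0.6, 0.7, 0.8 and 0.9. T4.09 therefore carries the same artefact in its improving direction.

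**Step 4: select on screening, subtract Day 1.** The expected change becomes (r_SB − r_SW) × λ × SD, where r_SB is the screening-to-Day 1 correlation and r_SW the screening-to-visit correlation. If the two are equal, this is zero; simulation gave 0.00.

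For decaying correlation, take r = p + a × 0.95^weeks, screening 4 weeks before Day 1, and half the children low (λ = 0.798).

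| p, a | Week 12: Day 1 selection | Week 12: screening selection | Week 52: Day 1 selection | Week 52: screening selection |
|---|---|---|---|---|
| 0.7, 0.1 | 0.20 | 0.03 | 0.23 | 0.06 |
| 0.6, 0.2 | 0.23 | 0.06 | 0.31 | 0.12 |
| 0.5, 0.3 | 0.27 | 0.09 | 0.38 | 0.18 |

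Worked example, middle row at Week 12: r_SB = 0.6 + 0.2 × 0.95⁴ = 0.763, Day 1-to-visit r = 0.6 + 0.2 × 0.95¹² = 0.708, and r_SW = 0.6 + 0.2 × 0.95¹⁶ = 0.688. Day 1 selection gives (1 − 0.708) × 0.798 = 0.23; screening selection gives (0.763 − 0.688) × 0.798 = 0.06. At Week 52 the exponents 12 and 16 become 52 and 56.

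**The case against.** The strongest case on the other side has five parts.

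- **Other displays exist.** A reader might infer that children outside the subset are never shown, or that nothing in the trial can separate the artefact from the drug. The documents do not support either. T4.06 and T4.09 cover all subjects and show worsening as well as improving shifts. Two pre-dose samples reveal variability without drug. Results by visit also help: under constant correlation the artefact is complete at the first visit, so later movement is partly interpretable. These are real but partial checks. The shift tables give no magnitude and use the same baseline, no planned summary compares screening with Day 1, and under decaying correlation the artefact grows with time.
- **The two values are not always Day 1.** If Day 1 is missing, the screening value becomes baseline. The same value still selects and is subtracted, so the problem remains.
- **The size is assumed.** This stands in full. With an assumed 14 low children (half of 28), the standard error of mean change is the square root of [(1 − r)² × (1 − 2/π) + 1 − r²]/14, about 0.20, 0.16 and 0.12 SD for r = 0.7, 0.8 and 0.9. The bias is then 0.7 to 1.2 standard errors, comparable to sampling noise. But noise has no preferred direction, whereas this bias does.
- **Everything is descriptive and the primary objective is PK.** That is true and limits the consequences. It does not remove bias from a reported mean or median.
- **Children with normal values cannot normalize, so a subset is sensible.** Agreed. The difficulty is only that the subset is chosen on the value subtracted.

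**Conclusion.** The point holds for numeric change and percentage change in C3, C4 and anti-dsDNA, and for ANA and CRP by the same mechanism. The direction, toward apparent benefit, follows from the selection and change rules for any within-child correlation below 1 when values are otherwise stable. The size rests on the assumed correlation, share low and normal model: about 0.05 to 0.46 SD with no drug effect.

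A reader might go further and infer that any observed improvement is an artefact, or that a particular number of mg/dL can be subtracted from the result. Neither follows. A real effect may be present as well, and the documents contain no SD or correlation from which to size a correction. Immunoglobulins and B cells, which belong to the same secondary endpoint, are summarized for all subjects and are unaffected.

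Separately, the subset restriction leaves the protocol's unrestricted ITT endpoint for these markers without a numeric summary, and this is undeclared.

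**What to change.** Amend SAP 11.1.4 and 11.1.5 as follows.

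1. Make the main display a by-visit summary of change and percentage change in C3, C4 and anti-dsDNA for all ITT subjects, as already planned for immunoglobulins and B cells. This restores the protocol endpoint and involves no selection on the subtracted value.
2. For the low or positive subset, define status from the screening sample and compute change from Day 1. Expected bias is zero under equal correlations. Under the decaying patterns above it falls to 0.03 to 0.09 SD at Week 12, against 0.20 to 0.27 SD. The remainder is larger at Week 52, so the all-subject display should carry the interpretation there.
3. Keep the Day 1-selected tables and figures as supportive, with a footnote that they include regression to the mean.

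If the restricted tables are to remain the main display, SAP 2.1 should declare that as a change from protocol 9.3.3.

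The cost is SAP wording, one selection flag and a few more tables from data already collected. The drawback is that a screening-defined subset will include some children who are normal or negative on Day 1, so it will not match the baseline groups in T1.15, T1.16, T4.06 and T4.09. A footnote should say so.

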11.1.5. Percentage Change from Baseline

Percentage change from baseline will be summarized by visit for the following:

- Immunoglobulin levels for all subjects [T4.01]
- B-cells for all subjects [T4.10]
- Autoantibody levels among subjects who were positive at baseline (ANA Index ≥80 titer; anti-dsDNA ≥ 30 IU/mL; CRP ≥ 4 mg/L) [T4.04]. Note that positive baseline assessments are assessed at a parameter level, e.g. the anti-dsDNA summary will include all subjects who were positive at baseline for anti-dsDNA.
- Complement levels among subjects with low values at baseline (C3<90 mg/dL; C4 < 13 mg/dL) [T4.07]. Note that low baseline assessments are assessed at a parameter level, e.g. the C3 summary will include all subjects who were low at baseline for C3.

The B cell subsets that will be summarized are CD19+ Total B cells, B cells CD20+, Memory CD20+ CD27+, Naïve CD20+ CD27- and Plasmablasts CD27b CD38b.

No statistical tests will be performed.

Figures of median percentage change from baseline (+/- Interquartile Range) will be produced by visit for:

- Immunoglobulin levels for all subjects [F4.01]
- B-cells for all subjects [F4.05]
- Autoantibody levels among subjects who were positive at baseline (as described above) [F4.02].
- Complement levels among subjects with low values at baseline (as described above) [F4.03].

11.2. Other Pharmacodynamic and Biomarker Analyses

Shift tables will be used to summarize the shifts from baseline in immunoglobulins [T4.03], autoantibodies [T4.06] and complement [T4.09] by visit.

11.2.1. Endpoint / Variables

Changes in biomarker category (Positive vs Negative; Low vs Normal/High) will be the endpoint.

11.2.2. Population of Interest

The biomarker analyses will be based on the ITT population.

11.2.3. Strategy for Intercurrent (Post-Randomization) Events

The analyses will be performed on the observed data. No imputation will be carried out for missing data.

11.2.4. Statistical Analysis

For Immunoglobulins (IgG, IgA, and IgM), baseline data will be summarized as the number and percentage of subjects who were low (<LLN) or normal/high (>=LLN). For post-baseline visits, the data will be summarized by the baseline status. Among subjects who were low at baseline, the shifts presented will be 'low to normal/high' or 'no change'. Among subjects who were normal/high at baseline, the shifts presented will be 'normal/high to low' or 'no change'.

For ANA titer, anti-dsDNA and C-Reactive Protein (CRP), baseline data will be summarized as the number and percentage of subjects who were positive (ANA Index ≥80 titer; Anti-dsDNA >=30 IU/mL; CRP >=4 mg/L) or negative (ANA Index <80 titer; Anti-dsDNA <30 IU/mL; CRP <4 mg/L) at baseline. Among subjects who were positive at baseline, the shifts presented will be 'positive to negative' or 'no change'. Among subjects who were negative at baseline, the shifts presented will be 'negative to positive' or 'no change'.

For serum complement C3 and C4, baseline data will be summarized as the number and percentage of subjects who were low (C3 <90 mg/dL; C4 <13 mg/dL) or normal/high (C3 ≥90 mg/dL; C4 ≥13 mg/dL) at baseline. Among subjects who were low at baseline, the shifts presented will be 'low to normal/high' or 'no change'. Among subjects who were normal/high at baseline, the shifts presented will be 'normal/high to low' or 'no change'. Note that the baseline categories presented above are for paediatric subjects. If a subject turns 18 during the study, any visits following their 18th birthday will be flagged using adult Normal Ranges. No statistical tests will be performed.

13. APPENDICES

13.1. Appendix 1: Assessment Windows

13.1.1. Definitions of Assessment Windows for Analyses

The data is analysed as per the planned visit assignment.

Exit/withdrawal and unscheduled visits will be slotted to the appropriate planned visit. The assigned visit is based on the interval in which the Study Day for the exit/withdrawal or unscheduled visit falls according to intervals (inclusive) provided below. For completeness, the table also includes visits which are not slotted; these visits will have 'N/A' for 'not available' listed for the Interval Start and End Day.

Analysis	Parameter	Target ¹	Analysis	Analysis Window		Analysis Timepoint
Set / Domain	(if applicable)		Beginning Timepoint	Ending Timepoint	Timepoint Number	
All	NA	Day -35	N/A	N/A	10	Screening
Cohort 1 ar	d Cohort 3	_L			I.	
All	All	Day 1	N/A	N/A	20	Week 0 (Day 1)
		Day 8	2	11	30	Week 1 (Day 8/11)
		Day 15	12	21	40	Week 2 (Day 15/21)
		Day 29	22	42	50	Week 4 (Day 29/31)
		Day 57	43	70	60	Week 8 (Day 57/61)
		Day 85	71	98	70	Week 12 (Day 85/81)
		Day 113	99	126	80	Week 16
		Day 141	127	154	90	Week 20
		Day 169	155	189	100	Week 24
		Day 211	190	231	110	Week 30
		Day 253	232	280	120	Week 36
		Day 309	281	336	130	Week 44
		Day 365	337	378	140	Week 52
		Day 421	N/A	N/A	175	8 Week Follow-up ²
		Day 477	N/A	N/A	185	16 Week Follow-up ³
Cohort 2						
All	All	Day 1	N/A	N/A	20	Week 0 (Day 1)
		Day 11	2	15	30	Week 1 (Day 8/11)
		Day 21	16	25	40	Week 2 (Day 15/21)
		Day 31	26	45	50	Week 4 (Day 29/31)
		Day 61	46	70	60	Week 8 (Day 57/61)
		Day 81	71	96	70	Week 12 (Day 85/81)
		Day 113	97	126	80	Week 16
		Day 141	127	154	90	Week 20
		Day 169	155	189	100	Week 24

CONFIDENTIAL

200908

Analysis Parameter Set / (if Domain applicable)		Target ¹	Analysis Window		Analysis	Analysis Timepoint
			Beginning Timepoint	Ending Timepoint	Timepoint Number	
		Day 211	190	231	110	Week 30
		Day 253	232	280	120	Week 36
		Day 309	281	336	130	Week 44
		Day 365	337	378	140	Week 52
		Day 421	N/A	N/A	175	8 Week Follow-up ²
		Day 477	N/A	N/A	185	16 Week Follow-up ³

Note:

¹ Study Day with Baseline/Treatment Start Date as Day 1.

²The 8-week follow-up occurs 8 weeks after Week 52, or 8 weeks after early withdrawal or 8 weeks after last dose for subjects who withdraw from Part A and do not enter Part B.

³ The 16-week follow-up occurs 16 weeks after Week 52, or 16 weeks after early withdrawal or 16 weeks after last dose for subjects who withdraw from Part A and do not enter Part B.

